Endpoints	
 • Diagnostic Yield: Defined as the percentage of procedures that either confirmed a diagnosis from previous studies, or established a new definitive diagnosis at the anatomical location identified in previous studies or findings that could explain the clinical symptoms • Therapeutic Yield: Defined as the percentage of patients with any endoscopic intervention / therapy with the exception of biopsies • Total procedure time: (starting with oral /anal insertion until final withdrawal of the device) • Total therapeutic intervention time • Total small bowel enteroscopy rate: Defined as complete evaluation of the small bowel either with a single approach or combined anterograde and retrograde approach (if complete small bowel enteroscopy is intended anyway) • Endoscopic success rate • Safety: Incidence (% of subjects) and frequency (no. of subjects) with device or procedure related Serious Adverse Events (SAEs) and Device Deficiencies (DD) observed during/after the procedure • User feedback and assessment of handling characteristics of the device
Study Design	International, multicenter, open label, non-randomized, prospective, observational study.
Sample Size	260 subjects will be enrolled into this registry including an expected rate of 5% of losses-to-follow-up during study conduct. The first 5 procedures for each investigator will be performed to get used to the device. Data on these “learning curve” procedures will be captured and analyzed separately. The dataset for final analysis (e.g. procedure time, rate of SAEs etc.) will include 260 cases from procedure #6 onwards in order to account for a learning curve effect. The sponsor plans to activate 12 sites with one or two investigators at each site. Each site shall enroll up to 22 subjects (notwithstanding the learning curve cases) to allow for the same quota per site. Overall approximately 335 subjects will be enrolled (including cases for the learning curve).

Clinical Investigation Plan

CIP Reference No.:2018-GI (OEKG) -01. The **SAMISEN** study - Final Version 02 - Date 23th April 2019

Timelines	Study Start (Enrollment of First Patient) is planned for May/June2019. Enrollment period: 1 year (until May/June 2020). Study closure: Q2/2020.

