3.3.6 Sample size

A total of 260 subjects shall be enrolled into this registry. This number factors in an expected drop-out-rate of 5%. Taking into account a drop-out-rate of 5% data from a total of 245 patients is expected to be available for statistical endpoints analyses.

With a sample size of 245 patients, the SAE rate can be estimated with a precision (i.e. width of the 95% confidence interval for the SAE rate) as shown in the following table.

Clinical Investigation Plan

CIP Reference No.:2018-GI (OEKG) -01. The **SAMISEN** study - Final Version 02 - Date 23th April 2019

Table 1 Precision of estimations of the rate of patients with at least one SAE

Sample size N	Patients with SAE	Rate of patients with SAE	95% CI (Clopper- Pearson)
245	5	2.0%	0.7% - 4.7%
245	10	4.1%	2.0% - 7.4%
245	15	6.1%	3.5% - 9.9%
245	20	8.2%	5.1% - 12.3%
245	25	10.2%	6.7% - 14.7%
245	30	12.2%	8.4% - 17.0%

As historical control, a SAE rate of 8% is considered (upper limit of the accepted SAE rate for patients undergoing deep enteroscopy according to the guideline (Rondonotti et al. 2018)).

In addition, to reflect the learning curve of each individual investigator, the first 5 patients per investigator will be considered training patients to become familiar with the handling and usage. All information of these “training patients” will be documented in the eCRF. These will be analyzed separately. 12 clinical sites in Germany, Belgium, France, Netherland, Italy, Denmark, Norway and Finland will be approached. At each site there will be either one or two investigators. Based on current information there will be approx. 15 investigators participating. Adding patients from the learning curve ($15 \times 5 = 75$) and the 260 study patient’s counting towards the endpoints together this study will enroll approximately 335 patients in total.

The enrolment period starts in May/June 2019 and will stop once the expected number of patients per site is reached. This “Last-Patient-In” (end of recruitment) is expected in May/June 2020.

Each site with two investigators shall take every effort to enroll a balanced number of patients per investigator.

Statistical Analyses will be performed with SAS software version 9.4 (SAS Institute Inc., Cary, NC, USA).

Clinical Investigation Plan

CIP Reference No.:2018-GI (OEKG) -01. The **SAMISEN** study - Final Version 02 - Date 23th April 2019

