2.2 Flow chart of study activities

2.3 Study Objectives

The primary endpoint of this study is the assessment of the rate of serious adverse events to show a non-inferiority to preceding generations of balloon assisted enteroscopes. Thus, the observed rate of serious adverse events will be computed alongside it's 95% Clopper-Pearson confidence interval. If the upper confidence limit will be 8% or less, non-inferiority will be concluded.

Secondary objectives are the description of the following parameters:

- Reaching the anatomical region of interest
- Therapeutic yield
- Total procedure time
- Total small bowel enteroscopy rate
- User feedback
- Safety profile
- Effect of the learning curve

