3.6 Efficacy Analysis

The following efficacy analyses will be performed based on the cITT population and on the ITT population as sensitivity analysis:

- The anatomical success rate (number of cases in which the suspected anatomical region is reached compared to all attempts) will be computed alongside with its 95% Clopper-Pearson confidence interval.
- The therapeutic yield (percentage of patients with any endoscopic intervention/therapy with exception of biopsies) will be presented alongside its 95% Clopper-Pearson confidence interval.
- The total procedure time (period in minutes needed to complete the procedure) will be summarized descriptively.
- The total therapeutic intervention time will be summarized descriptively.
- The total small bowel enteroscopy rate (number of complete evaluations of the small bowel divided by all attempts to reach the small bowel) will be computed alongside its 95% Clopper-Pearson confidence intervals.
- The outcomes for the items in the user feedback for the judgement of handling characteristics and other aspects will be tabulated in frequency tables.
- Diagnostic Yield (i.e. diagnosis, that explains findings from previous imaging or establishes a new diagnosis, that could explain clinical symptoms, that indicated PSE)
 - Diagnostic Yield is defined as the difference of proportion of patients for which a diagnosis was made and the proportion of patients with prior positive imaging (VKE, MRI, other)

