3.7 Safety Analysis

3.7.1 Primary Safety Analysis

The primary safety analysis of the serious adverse events will be based on the cSAF. The rate of serious adverse events during and after enteroscopy procedure will be computed as the number of such serious adverse events divided by the number of patients in the cSAF. A 95% Clopper-Pearson confidence interval will be computed for the rate to assess the variability of the estimate. In case of an upper 95% confidence limit von 8% or below, non-inferiority to preceding generations of balloon assisted enteroscopes will be concluded.

The primary endpoint will be assessed in the core SAF as primary analysis. As secondary analyses, the primary endpoint will be assessed for the SAF, ITT and core ITT as well as for training patients only.

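### The SAP names the learning-curve effect as a secondary objective but plans a training-only result for the SAE rate alone; efficacy, procedure-time and AE tables show training patients only inside the pooled set.

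*SAP*

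**What the plan says.** **Protocol.** Section 3.3.6 states that "the first 5 patients per investigator will be considered training patients", and then: "These will be analyzed separately". The trial summary makes the same commitment; data on the learning-curve "procedures will be captured and analyzed separately". Neither place limits this to safety. On numbers, section 3.3.6 says: "Based on current information there will be approx. 15 investigators participating". That gives 75 training patients, 260 core patients and about 335 in total.

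**SAP objectives.** Section 2.3 introduces its list with "Secondary objectives are the description of the following parameters", and the last item is "Effect of the learning curve". No variable or method is attached to that item.

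**SAP populations.** Section 3.1 defines cSAF and cITT without the training patients, and SAF and ITT with them. There is no training-only set.

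**SAP analyses.**
- Section 3.6 runs all efficacy analyses "based on the cITT population and on the ITT population as sensitivity analysis".
- In the table list (3.9), tables 11.2.1 to 11.2.4 use ITT and cITT. Procedure time (11.1.7.6) and the adverse-event tables 11.3.1.1 to 11.3.1.8.2 use SAF and cSAF. The SAE subgroup table uses cSAF.
- Section 3.7.1 assesses the primary SAE endpoint in several sets "as well as for training patients only". This is the only training-only analysis in the SAP, and the table list has no entry labelled for it.
- Section 3.8 plans no other analyses.

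**The concern.** A learning curve is described by setting early cases beside later ones. For efficacy and procedure time, the SAP instead sets later cases beside all cases. The two columns share about 78% of their patients (260/335), so they will look alike even when training and core patients differ a good deal. A reader looking in those tables for the objective in SAP 2.3 could conclude that there is little or no learning curve, when the display itself has shrunk the difference.

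The protocol sets about 75 patients apart because it expects early cases to differ. If the SAP is followed as written, anatomical success, total enteroscopy rate, therapeutic and diagnostic yield, procedure and intervention time, and user feedback will have no separate training result. Any such analysis would then be devised after the data are in.

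**Working it through.** **Inputs.** Protocol 3.3.6 gives 5 training patients per investigator, about 15 investigators and 260 core patients. The trial summary plans 12 sites with one or two investigators each, so 12 to 24 investigators are possible.

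**The plan's own figures.** 15 × 5 = 75 training patients, and 260 + 75 = 335 in total. Both reproduce.

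**Dilution.** Let *w* be the training share of the pooled set. For any mean or proportion,

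pooled = *w* × training + (1 − *w*) × core,

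so pooled − core = *w* × (training − core).

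The 15-minute and 20-point differences below are assumptions; the documents give no training or core values.

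| Investigators | Training / pooled | *w* | 15 min appears as | 20 points appear as |
|---|---|---|---|---|
| 12 | 60/320 | 18.8% | 2.8 min | 3.8 points |
| 15 | 75/335 | 22.4% | 3.4 min | 4.5 points |
| 24 | 120/380 | 31.6% | 4.7 min | 6.3 points |

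With the 245 evaluable core patients of protocol 3.3.6 and all 75 training patients, *w* = 75/320 = 23.4%, so the size barely changes.

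**Example for a success rate (assumed 80% core, 60% training).** Core 208/260 = 80.0%, training 45/75 = 60.0%, pooled 253/335 = 75.5%.
- Planned display: ITT 75.5% (Clopper-Pearson 70.6% to 80.0%) beside cITT 80.0% (74.6% to 84.7%).
- Disjoint display: training 60.0% (48.0% to 71.1%) beside core 80.0%. The standard error of the difference is √(0.6×0.4/75 + 0.8×0.2/260) = 6.18 points, so the difference is 20 points ± 1.96 × 6.18 = ± 12.1 points.
- With an assumed 70% in training, the standard error is √(0.7×0.3/75 + 0.8×0.2/260) = 5.84 points. The difference is then 10 ± 11.5 points, and the interval includes zero.

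These half-widths treat patients as independent and ignore grouping by investigator.

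**What subtraction recovers.** The sets are nested, so training counts equal pooled minus core counts, and exact intervals follow. For a continuous variable with pooled *n, m, s*, core *n_c, m_c, s_c* and training size *n_t*:

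*m_t* = (*n m* − *n_c m_c*) / *n_t*

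(*n_t* − 1) *s_t*² = (*n* − 1) *s*² + *n m*² − (*n_c* − 1) *s_c*² − *n_c m_c*² − *n_t m_t*²

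In one simulated data set (75 training, 260 core), these formulas returned the true training mean and SD, 68.59 and 21.24. The medians in the same data set differed by 23.4 between training and core but by only 3.2 between pooled and core. The training median and quartiles cannot be obtained from the two summary columns, although SAP 3.5 plans medians and quartiles for quantitative variables.

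**The case against.** A reader might infer that the learning-curve objective cannot be answered for efficacy. The documents do not support that. The objective is descriptive, and protocol 4.1.2 rules out hypothesis tests for efficacy. Training counts, rates, means and SDs follow by subtraction from the planned tables. The general listings carry patient ID and analysis population, so training patients are identifiable. What is missing is a specified output.

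Nor does the SAP present ITT against cITT as its learning-curve comparison. It calls ITT a sensitivity analysis, which is a legitimate check on whether including the training cases changes the results.

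It would also go too far to say that the SAP contradicts the protocol. The core sets do what the trial summary asks, which is to keep the final dataset to later cases. The protocol's commitment to a separate analysis names no endpoints, and section 4 leaves detail to the SAP. Incomplete implementation is the fair description.

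The dilution argument does not apply to the primary SAE rate, because SAP 3.7.1 commits to a training-only result there.

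Finally, about 75 training patients give imprecise differences, and a wide interval could itself be misread as showing no learning effect.

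All of this stands as a limit on the point. It does not remove the gap. A named objective should not depend on readers subtracting columns, and subtraction does not yield the medians and quartiles.

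**Conclusion.** The point holds as an omission in the SAP and a weakness of the planned display. For efficacy, procedure time, user feedback and adverse events, no training-only result is planned, although SAP 2.3 and the protocol both call for training patients to be looked at in their own right. The planned columns show about 22% of any training-core difference, or 19% to 32% across 12 to 24 investigators.

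The dilution factor rests only on the planned numbers and on 5 training patients per investigator. The 15-minute and success-rate examples rest on assumed values. The primary analysis in cSAF and its non-inferiority rule are not affected.

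**What to change.** 1. In SAP 3.1, define a training set as the first 5 patients per investigator. The trial summary counts the first 5 procedures while protocol 3.3.6 counts patients, so state which unit applies when a patient has two procedures.
2. In the efficacy, procedure-time, user-feedback and adverse-event tables, add a training-only column beside the core column. Add an entry in SAP 3.9 for the training-only SAE rate already promised in 3.7.1.
3. For SAE rate, procedure time, anatomical success and total enteroscopy rate, give the training-minus-core difference with a descriptive 95% confidence interval that allows for clustering by investigator. Each investigator is expected to contribute to both sets, so a model with investigator as a stratum or random effect is a natural choice.
4. Keep the pooled ITT and SAF results as the sensitivity analysis if wanted, and state in SAP 2.3 that the training and core columns address the learning-curve objective.

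**Cost.** The data are already captured in the eCRF, so this means modest extra programming and output. The intervals will be wide, about ±12 points on a success rate under the rates assumed above and before allowing for clustering. The comparison should therefore stay descriptive, with a note that an interval including zero does not show the absence of a learning effect.

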2.4 Primary and secondary variables

Primary efficacy variable:

The rate of serious adverse events during and after enteroscopy will constitute the primary endpoint for this study.

Secondary efficacy variables:

- Reaching the anatomical region of interest: The rate of successfully reaching the suspected anatomical target region (either by antegrade or by retrograde route) compared to all attempts represents the endpoint 'anatomical success rate'.
- Therapeutic yield: Defined as the percentage of patients with any endoscopic intervention / therapy with the exception of biopsies. (Sethi et al. 2014; Prachayakul et al. 2013; Sanaka et al. 2012)
- Total procedure time: Period in minutes needed to complete the procedure.
- Total therapeutic intervention time: Period in minutes dedicated to therapeutic intervention(s).
- Total small bowel enteroscopy rate: Defined as complete evaluation of the small bowel either with a single approach or combined anterograde and retrograde approach (if complete small bowel enteroscopy is intended anyway (Committee et al. 2015; Gerson et al. 2015).
- Diagnostic Yield (i.e. diagnosis, that explains findings from previous imaging or establishes a new diagnosis, that could explain clinical symptoms, that indicated PSE)
- User feedback and judgment of handling characteristics and other aspects: User feedback and assessment of handling characteristics and other logistical aspects regarding:
 - Handling of PowerSpiral
 - Instrument insertion of PowerSpiral
 - Precision of positioning during therapy of PowerSpiral
 - Time needed for procedure of PowerSpiral
 - Staff and resource needed for procedure of PowerSpiral
- Serious adverse events (PS product related)
- Adverse events during enteroscopy procedure and adverse events (PS product related)

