Clinical Investigation Plan

CIP Reference No.:2018-GI (OEKG) -01. The **SAMISEN** study - Final Version 02 - Date 23th April 2019

The main objective of the SAMISEN study is to assess the performance and safety of diagnostic and therapeutic procedures with the newly designed Olympus Motorized Spiral Enteroscope (INTESTINAL VIDEOSCOPE OLYMPUS PSF-1 and SINGLE USE POWERSPIRAL TUBE DPST-1) system in combination with the motor control unit (POWER SPIRAL CONTROL UNIT PSCU). All Serious Adverse Events (SAE) observed in this study will be documented so the overall SAE rate as well as the number of individual types of complications (bleeding, pancreatitis etc.) can be calculated.

The very recent publication of Rondonotti (Rondonotti et al. 2018) for device-assisted enteroscopy for diagnosis and treatment of small-bowel disorders represents an excellent source for comparison. Hence this study is designed as a prospective study without control group. The resulting SAE rate will be compared to the historical data from this ESGE Technical Review (Rondonotti et al. 2018).

The performance will be characterized by calculating the Diagnostic and Therapeutic Yield, Total Procedure Time, time needed for Therapeutic Intervention, Total Small Bowel Enteroscopy Rate and user feedback on device handling.

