3.1.3 Variables in the Clinical Investigation

It is a prospective and observational Registry without any additional procedure beyond clinical practice. The small-bowel enteroscopy has to be performed according the medical standard. Serious Adverse Events (SAE) and Device Deficiencies (DD) must be documented.

The main safety endpoint is a combined one, capturing all SAEs / DDs captured during the study period. The definition is:

- **Safety:** Incidence (% of subjects) and frequency (no. of subjects) of device or procedure related Serious Adverse Events (SAEs) and Device Deficiencies (DD) observed during/after the procedure.

As main efficacy endpoint we will determine in how many cases the suspected anatomical target lesion can be reached. The definition is:

- **Diagnostic Yield:** Defined as the percentage of procedures that either confirmed a diagnosis from previous studies, or established a new definitive diagnosis at the anatomical location identified in previous studies or findings that could explain the clinical symptoms (Sethi et al. 2014; Prachayakul et al. 2013; Lenz, Roggel, and Domagk 2013; Sanaka et al. 2012).

Clinical Investigation Plan

CIP Reference No.:2018-GI (OEKG) -01. The **SAMISEN** study - Final Version 02 - Date 23th April 2019

Further efficacy endpoints cover performance aspects of the device. The definitions are:

- **Therapeutic Yield:** Defined as the percentage of patients with any endoscopic intervention / therapy with the exception of biopsies. (Sethi et al. 2014; Prachayakul et al. 2013; Sanaka et al. 2012).
- **Total procedure time:** the time from oral (anal) insertion until withdrawal of the device.
- **Total therapeutic intervention time:** The part of the procedure dedicated to therapeutic maneuvers (biopsies will not be considered here).
- **Total small bowel enteroscopy rate:** Defined as complete evaluation of the small bowel either with a single approach or combined anterograde and retrograde approach (if complete small bowel enteroscopy is intended anyway (Committee et al. 2015; Gerson et al. 2015).
- **User feedback** and judgment of handling characteristics and other aspects.

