11.2 Documentation

11.2.1 (Serious) Adverse Events / Adverse Device Effects

Independent from a possible relation to the investigational device, every AE spontaneously reported by the subject or observed by the investigator has to be reported on the appropriate page of the case report form. Furthermore, the investigator shall actively ask the subject about the occurrence of any (S)AE at each visit and note any abnormal laboratory findings. For each adverse event the following information should be documented:

- Description of the event (diagnosis and symptoms in verbatim terms),
- Outcome,
- Seriousness,
- Duration (start date and stop date),
- Causal relationship to the investigational device.

Causality assessment will be done by the investigator using a 5-category system (no related / unlikely / possible / probable / causal relationship).

- Any therapy or corrective action initiated including.

The results of any complementary tests performed (laboratory tests, ECG, etc.) must be pseudonymized by the investigator prior to forwarding information to the sponsor. A period of 4 weeks for follow up of AEs after the subject has routinely completed or prematurely terminated the study seems sufficient. This means that any additional information needed to assess the (S)AE should be collected and documented in the respective CRF within one month after occurrence.

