3.7.2 Adverse Events

The frequencies of adverse events, serious adverse events and device deficiencies will be reported in summary tables. These tables will show the number of subjects per group presenting a (serious) adverse event and the incidence of its occurrence.

Tabulations will be provided for system organ class and stratified by relation to the investigational product. Any withdrawals from the study due to adverse events will be reported. All measures taken due to adverse events will be reported.

AEs of special interest

- Number of patients with pancreatitis
- Number of patients with bleeding
- Number of patients with perforation
- Number of patients with complications associated with sedation/anesthesia
- Number of patients with other complications

For pre-treatment events summary tables and listings will be provided.

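### The protocol's main safety endpoint (related SAEs and device deficiencies) is never estimated with an interval in the SAP, and the documents do not agree on one rate to hold against 8%

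*SAP*

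**What the plan says.** **Protocol, endpoint definition.** Section 3.1.3 introduces the endpoint thus: "The main safety endpoint is a combined one, capturing all SAEs / DDs captured during the study period". The definition that follows is narrower: the percentage and number of subjects "of device or procedure related Serious Adverse Events (SAEs) and Device Deficiencies (DD) observed during/after the procedure". The trial summary repeats the narrower wording.

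**Protocol, benchmark.** Section 1.2 has all SAEs documented "so the overall SAE rate as well as the number of individual types of complications" can be calculated, and plans to compare the SAE rate with a published technical review. Section 3.3.6 takes an SAE rate of 8% as historical control, and its Table 1 gives precision for patients with at least one SAE. Neither section mentions relatedness or device deficiencies.

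**Protocol, safety variables.** Section 4.1.3 lists SAEs during and after the procedure and, as a separate item, SAEs related to procedure or product. Section 11.2.1 lists, for each adverse event, "Causal relationship to the investigational device"; relationship to the procedure is not in that list.

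**SAP.** Section 2.4 states: "The rate of serious adverse events during and after enteroscopy will constitute the primary endpoint for this study". Sections 2.3 and 3.7.1 apply the 8% rule to that rate. Related SAEs appear only as a secondary variable, in the item that begins "Serious adverse events (PS product related", so the procedure-related part of protocol 4.1.3 is gone. On deficiencies, section 3.7.2 says: "The frequencies of adverse events, serious adverse events and device deficiencies will be reported in summary tables". Section 3.9 adds 95% intervals to frequency tables for the primary endpoint only.

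**The concern.** The study has one pass/fail conclusion, and it depends on which patients count as affected. Across the two documents there are at least three candidates: patients with any SAE, patients with a device- or procedure-related SAE, and patients with a related SAE or a device deficiency. The SAP cites protocol version 02 as its basis but does not say why its primary endpoint differs from the protocol's main safety endpoint. Under the present plan, a reader of the final report could not find the protocol's endpoint as a rate with an interval, and could not tell from the documents why 8% is the right yardstick for whichever rate is shown.

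**Working it through.** **Inputs.** Evaluable n = 245 of 260 (protocol 3.3.6); 260 analysable cases (protocol summary); two-sided 95% Clopper-Pearson limits (SAP 2.3, 3.5, 3.7.1); pass if the upper limit is at most 8%. The documents give no related share and no deficiency rate. Protocol 11.2.2 mentions two deficiencies in earlier studies, without a denominator. Both quantities are therefore assumed below, over a range.

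**Step 1: reproduce Table 1.** For x patients out of n, the lower limit is the 2.5% quantile of Beta(x, n − x + 1) and the upper limit is the 97.5% quantile of Beta(x + 1, n − x). With n = 245:

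| x | Computed interval | Table 1 |
|---|---|---|
| 5 | 0.67–4.70% | 0.7–4.7% |
| 10 | 1.97–7.38% | 2.0–7.4% |
| 15 | 3.47–9.90% | 3.5–9.9% |
| 20 | 5.06–12.33% | 5.1–12.3% |
| 25 | 6.71–14.69% | 6.7–14.7% |
| 30 | 8.42–17.02% | 8.4–17.0% |

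All six rows agree.

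**Step 2: the pass boundary.**
- n = 245: 11 patients give an upper limit of 7.89% (pass); 12 give 8.40% (fail).
- n = 260: 12 patients give 7.92% (pass); 13 give 8.40% (fail).

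**Step 3: the same data under different definitions (assumed counts, n = 245).**

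| Case | Definition | Patients | Upper limit | Result |
|---|---|---|---|---|
| A | All SAEs (SAP) | 13 | 8.90% | fail |
| A | Related SAEs only | 10 | 7.38% | pass |
| A | Related SAEs, plus 2 with a deficiency only | 10 + 2 = 12 | 8.40% | fail |
| B | All SAEs (SAP), all of them related | 11 | 7.89% | pass |
| B | Related SAEs, plus 1 with a deficiency only | 11 + 1 = 12 | 8.40% | fail |

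In case A the SAP rule is stricter than a related-only rule. In case B it is more lenient than the composite.

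**Step 4: the chance of passing.** P(pass) = P(X ≤ boundary), X binomial with the true rate:

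| True rate | n = 245 | n = 260 |
|---|---|---|
| 3% | 0.932 | 0.948 |
| 4% | 0.722 | 0.756 |
| 5% | 0.430 | 0.460 |
| 6% | 0.197 | 0.213 |
| 7% | 0.072 | 0.077 |

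One percentage point more or less in the counted rate moves the chance of passing by about 0.2 to 0.3 between 3% and 6%.

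**Step 5: composite against SAP rate.** Let a be the rate of patients with any SAE, r the related share, and d the deficiency rate among patients without a related SAE. The composite rate is q = ar + (1 − ar)d. Take a = 5%, for which the SAP rule passes with probability 0.430 at n = 245:
- r = 0.5, d = 0: q = 2.5%, P(pass) = 0.978.
- r = 0.75, d = 1%: q = 0.0375 + 0.9625 × 0.01 = 4.71%, P(pass) = 0.513.
- r = 0.75, d = 2%: q = 0.0375 + 0.9625 × 0.02 = 5.68%, P(pass) = 0.261.
- r = 1, d = 4%: q = 0.05 + 0.95 × 0.04 = 8.8%, P(pass) = 0.007.

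The two rates are equal when (1 − ar)d = a(1 − r). For a = 5% and r = 0.75 this gives d = 0.0125 / 0.9625 = 1.3%. Below that deficiency rate the SAP endpoint is the harder test; above it, the composite is.

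**The case against.** The strongest reply is that the SAP tests the right event type. Protocol 1.2, 3.3.6 and Table 1 all speak of the SAE rate without a filter, and the sentence that opens the endpoint definition in 3.1.3 says all SAEs and deficiencies. That stands. A reader might infer that the SAP holds 8% against a quantity foreign to the protocol; the documents do not support this, because the protocol never ties 8% to the composite. On relatedness, the contradiction lies inside the protocol. The omission of device deficiencies is the SAP's own departure from both wordings in 3.1.3.

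A reader might also infer that the definition could be picked once the data are in. SAP 2.3, 2.4 and 3.7.1 name the same event type and tie the rule to it, so within the SAP no such choice is open.

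Third, counting all SAEs is stricter than counting related ones: at patient level, a pass on all SAEs implies a pass on related SAEs. Participation lasts about two days to a week (protocol 3.3.5), which leaves little time for unrelated events. This also stands, but it does not cover deficiencies, which work in the other direction.

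Finally, much of the raw material is tabulated. SAP 3.7.2 and table 11.3.1.8.2 cover pancreatitis, bleeding, perforation and sedation complications; tables 11.3.1.4.2 and 11.3.1.7.2 show SAE relatedness and device causality separately; deficiencies get summary tables. It would go too far to say that procedure-related events are lost: the CRF may record that relationship, and it cannot be seen here. What is missing is a specified patient-level rate with an interval for related SAEs, for deficiencies and for the composite.

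**Conclusion.** The point holds as a conflict of definitions and an endpoint that is not estimated. The protocol defines its main safety endpoint one way and attaches the 8% benchmark to another quantity; the SAP follows the benchmark, leaves out deficiencies, narrows the related-SAE variable to product-related events, and gives no interval for the protocol's endpoint.

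The size is a matter of a few patients: the boundary is 11 of 245 or 12 of 260, and one to three patients classified differently reverse the result in the cases above. With a true SAE rate of 5%, related shares of 50–100% and deficiency rates of 0–4%, the chance of passing on the composite runs from 0.98 to 0.01, against 0.43 on the SAP endpoint. Those ranges are assumptions. So is the reading of the protocol endpoint as patients with at least one of either component.

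The figures do not show that the SAP rule is too lenient, nor that it is too strict; the direction cannot be known from the documents. That the SAP means SAEs of any cause is itself an inference, from the absence of a filter and from the separate listing of related SAEs. Severity: should be fixed.

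**What to change.** 1. Reconcile protocol 3.1.3 and 3.3.6 with SAP 2.3, 2.4 and 3.7.1. Name in both documents one rate held against 8%, defined on patients with at least one event, and state why 8% refers to that quantity. As written, protocol 3.3.6 ties it to patients with at least one SAE, with no relatedness filter. Moving the test to related SAEs alone would set a narrower numerator against that benchmark and would need its own justification. SAP 3.7.1 now divides the number of events by patients; the patient-level wording should replace this, since a Clopper-Pearson interval needs a count of patients.
2. In SAP 3.7.1, add named supportive analyses on the cSAF, each with a Clopper-Pearson interval: patients with at least one device- or procedure-related SAE; patients with at least one device deficiency; and the composite of protocol 3.1.3. State which causality categories count as related.
3. In protocol 3.1.3, remove the contradiction between the introductory sentence and the definition.
4. List relationship to the procedure in protocol 11.2.1 if the CRF does not already record it.

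Cost: wording in both documents and a few table rows, with no extra patients. If the CRF lacks the procedure relationship, one further item would have to be collected.
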